### 2.4.6.1 Analysis of JIA ACR30 response

Patients achieving JIA ACR30 [REDACTED] response for each dose regimen cohort, overall and by weight group, will be summarized by visit using counts, proportions and 95% CIs. The primary approach will be based on all observed data while the patient remains on treatment. No missing data will be imputed.

Additionally, for the summaries on the JIA ACR30 responses during the 12-week core treatment part, several different approaches will be used for the handling of treatment discontinuations and missing data.

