11.4.2.1 Analysis of primary efficacy endpoint(s)

Analysis of JIA ACR30 response is provided in this study section.

Patients achieving JIA ACR30 response for each dose regimen cohort, overall, and by weight group will be summarized by visit using counts, proportions and 95% CIs. All observed data, while the patient remains on treatment will be included in this analysis. No missing data will be imputed. Additionally, for the summaries on the JIA ACR 30 responses during the 12-week core treatment phase, several different approaches will be used for the handling of treatment discontinuations and missing data.

Non responder imputation:

In general, number of joints with active arthritis, number of joints with limited range of motion, and at least 3 of the remaining 4 ACR components at Baseline and a time point are required to determine responder status.

In this method of missing data handling, the data collected after treatment discontinuation will be set to missing. No imputation of missing post baseline values will be performed. Responder status will be determined using available data and patients will automatically become non responders for all time points beyond the time point they discontinued study treatment or for which there is insufficient data.

LOCF approach:

In this method of missing data handling, the missing data will be imputed using the LOCF procedure from the point of treatment discontinuation for all 6 ACR components for all visits post that point. Responder status will be determined using the imputed data.

In this approach, patients with insufficient data after imputation (ie, number of joints with active arthritis, number of joints with limited range of motion, and at least 3 of the remaining 4 ACR components) at baseline and a time point will be considered as non responders at that time point.

As observed including post discontinuation follow-up:

All observed data up to Week 12, including those collected after treatment discontinuation, will be included in this analysis. No missing data will be imputed.

Subgroup analyses:

No additional subgroup summaries are planned for the efficacy.

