## 2.4.6 Analyses of efficacy endpoints

Efficacy is considered as secondary in these studies, and will be summarized descriptively for each study (ie, disease type) separately.

Efficacy analyses will be done by dose regimen cohort and by weight group. Summaries on the non-selected doses will only include the data collected prior to the first dose adjustment to the selected dose. Data after the dose adjustment will be summarized separately ([Section 2.4.11](#)).

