***Subgroup analyses:***

No additional subgroup summaries are planned for efficacy.

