**2.4.6.2 Analyses of other efficacy endpoints**

JIA ACR30 core set variable scores and changes from baseline for each dose regimen cohort and weight group will be summarized by visit using means, standard errors, and corresponding 95% CIs. JIA ACR30 response using ESR instead of hs-CRP will be summarized using the same methods as described in the previous section.

JIA ACR50/70/90/100 responses will be summarized using the same methods as described above for JIA-ACR30.

Overall score and change from baseline in JADAS-27 will be summarized by visit (including number, mean, standard error, SD, median, minimum, and maximum) for each dose regimen cohort and weight group (if possible).

Proportions of patients with the low disease activity ( $JADAS-27 \leq 3.8$ ) and inactive disease activity ( $JADAS-27 \leq 1.0$ ) as defined based on JADAS-27 will be explored and summarized. The Kaplan-Meier plot for time to first onset of achieving low disease activity or achieving inactive disease will also be provided.

For the analyses of continuous endpoints including JIA ACR core set variables and JADAS-27, no data will be imputed and the analyses will be done based on data as observed while the patient remains on treatment.

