### **2.5.3 Missing data**

For categorical variables, patients with missing data are not included in calculations of percentages unless otherwise specified. When relevant, the number of patients with missing data is presented.

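### Extension ACR response rates are planned only as observed on treatment, although a Week-12 ACR30 gate removes non-responders in the dose-finding and second portions but not in the third

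*SAP*

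**What the plan says.** ACR30/50/70/90/100 response at Weeks 24 and 48, and at 24-week steps after that, is a listed extension endpoint (Protocol 9.2.2; SAP 2.1.5.2).

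Rules for summarising it:

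- SAP 2.4.6.1, by visit: "The primary approach will be based on all observed data while the patient remains on treatment. No missing data will be imputed". Protocol 11.4.2.1 agrees: "All observed data, while the patient remains on treatment will be included in this analysis".
- The alternatives (non-responder imputation, LOCF, and observed data including follow-up after discontinuation) are tied to the core part. SAP 2.4.6.1: "Additionally, for the summaries on the JIA ACR30 responses during the 12-week core treatment part, several different approaches will be used".
- SAP 2.4.6.2: "JIA ACR50/70/90/100 responses will be summarized using the same methods as described above for JIA-ACR30".
- SAP 2.5.3, for categorical variables: "patients with missing data are not included in calculations of percentages unless otherwise specified".
- SAP 2.4.6: "Efficacy analyses will be done by dose regimen cohort and by weight group". SAP 2.4.6.1 adds: "No additional subgroup summaries are planned for efficacy".
- SAP 2.4.6, for patients who later switch: "Summaries on the non-selected doses will only include the data collected prior to the first dose adjustment to the selected dose". Their later data are summarised separately.

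Who enters the extension: Protocol 1.2.2, 6.1 and Appendix C, and SAP 1.1, require an ACR30 response at Week 12 in the dose-finding and second portions. For the third portion, Protocol 6.1 and SAP 1.1 describe an 84-week extension with no response condition.

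**The concern.** In the first two portions the endpoint itself decides who stays in the denominator. A high extension ACR rate there is partly produced by the gate. Third-portion patients on the same regimen enter the same rows without that selection. After their Week-96 end-of-treatment (EOT) visit only gated patients remain, and the second interim analysis contains only the gated portions (SAP 3). A trend across visits can therefore reflect a change in patient mix.

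The observed rate is a legitimate summary if it is read as conditional on remaining on treatment. With no such label, no all-treated rate and no split by portion, a reader can take it as the long-term response of everyone treated.

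**Working it through.** **1. Planned numbers.** The documents' figures reproduce.

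- Total treated: about 72 in the first two portions + 28 in the third = 100.
- Third-portion weight-group cap: 0.70 × 28 = 19.6, stated as 20, which leaves 8 (Protocol 8.4).
- Gated patients starting on the selected regimen: 2 × 18 = 36 evaluable if one of the three tested regimens is selected. With an intermediate regimen, which the protocol summary allows, only second-portion patients start on it: 2 × 12 = 24.

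The visible documents give no Week-12 response rate and no dropout rate. Everything below is illustration, with an assumed Week-12 ACR30 rate p of 70, 80 or 90% and no other dropout.

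**2. Gated portions alone, no EOT record counted.** Let a share l of Week-12 responders lose response but stay on treatment. The observed rate is 1 − l and the all-treated rate is p(1 − l), so the ratio is 1/p whatever l is:

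- p = 70%: 1/0.7 = 1.43
- p = 80%: 1/0.8 = 1.25
- p = 90%: 1/0.9 = 1.11

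**3. Pooled row, g gated plus 28 ungated patients, no change of status.** Responders are (g + 28)p and patients on treatment are gp + 28. The all-treated rate is p.

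| p | g = 36 | g = 24 |
|---|---|---|
| 70% | 44.8/53.2 = 84% | 36.4/44.8 = 81% |
| 80% | 51.2/56.8 = 90% | 41.6/47.2 = 88% |
| 90% | 57.6/60.4 = 95% | 46.8/49.6 = 94% |

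This applies at Weeks 48 and 72. It applies at Week 96 only if the third portion's EOT record counts as on treatment (step 5).

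**4. Why the all-treated rate must also be shown by portion.** Third-portion non-responders may continue and respond later. If an assumed 25% of them do, the all-treated rate there is p + 0.25(1 − p) = 77.5, 85 or 92.5%, against p in the gated portions. A pooled all-treated rate would mix two stopping rules.

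**5. EOT records.** ACR status reaches the investigator only after Visit 12 (Protocol 1.2.1, footnote j). A Week-12 non-responder can therefore be dosed at Visit 12 and have EOT one or two weeks later (Protocol 1.2.2.1, footnote a). The next planned ACR visit is Week 24, and SAP 2.5.4 moves a discontinuation visit to the next planned assessment. SAP 2.1.5 by default includes efficacy data up to closeout. The on-treatment condition in 2.4.6.1 could narrow that, but the visible efficacy text does not define it. The safety epochs end 13 or 6 days after the last dose (SAP 2.1.4), one day before nominal EOT. With no status change, the gated Week-24 rate lies anywhere from p (all such records mapped there) to 100% (none). The same uncertainty affects the third portion at Week 96, two weeks after its Week-94 last dose (Protocol 1.2.2.3, footnote g).

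**6. Why imputation should not reach non-selected regimens after switching.** Take six patients: five respond, one is gated out, and nobody loses response. Keep the gated-out patient as a non-responder and drop patients as they switch. The rate runs 5/6 = 83%, then 1/2 = 50% after four switches, then 0/1 = 0% after five. The fall is an artefact.

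**The case against.** The strongest reply is that the study is open-label, has a PK primary endpoint and tests no hypothesis. Efficacy is secondary and descriptive, and much can be recovered from planned output. ACR results come with counts and 95% CIs. Disposition by cohort and weight group includes numbers treated, entering the extension and discontinuing (SAP 2.2). Missing counts are shown where relevant, and Week-12 non-responder imputation shows the loss at the gate. The second interim analysis already shows the gated portions without the third.

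Most of this stands as mitigation. It does not supply a split by portion in the pooled tables. Nor does it give a valid all-treated rate at an interim cut, because not everyone could have reached each visit. For example, the third interim analysis falls about one year after the last third-portion enrolment. The combined any-dose group in SAP 2.4.5 is described for safety only.

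Two further points stand. SAP 1.3, 1.5, 1.6, 2.4.11 and the Appendix C mock-ups are not visible and could contain a split or another denominator. Splitting by both portion and weight group could leave a third-portion cell of 8.

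A reader might infer from step 5 that gated-out patients' EOT records should be barred from Week 24 to avoid an apparent rise to Week 48. The documents do not support that. SAP 2.1.5 and 2.5.4 point towards including and mapping these records, and removing mostly non-responder records would raise the Week-24 rate and strengthen the selection. The finding is only that the interaction of the rules is unclear.

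**Conclusion.** The concern holds on the visible text, for patients who start on the selected regimen. Their extension ACR rates are planned only as observed on treatment. In the dose-finding and second portions those rates are conditional on a Week-12 response. Pooled rows mix gated and ungated patients until the third portion ends.

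The overstatement relative to an all-treated rate cannot be derived from the documents. The factors 1.43/1.25/1.11 and the pooled 81 to 95% rest on an assumed p and no other dropout. The pooled figures also assume no change of response status, and the factors assume that no EOT record is counted.

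A reader might infer a known bias, or damage to the study's main conclusion. Neither is supported: no Week-12 rate is stated, the primary endpoint is PK exposure, and there is no error rate to affect. Nor can it be said that the sponsor has no such analysis, only that none is visible. Whether the gate should differ between portions is a clinical rule, on which no view is taken.

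**What to change.** 1. For patients who started on the selected regimen, present extension ACR30 to ACR100 for the dose-finding and second portions together, separately from the third portion. Combine weight groups where cells are small.
2. Beside the observed rate, add by portion a non-responder rate over all treated patients who could have reached the visit by the data cut. Count discontinuation, including at the Week-12 gate, as non-response.
3. Do not apply that imputation to non-selected regimens after dose adjustment, or to post-adjustment summaries. Label those rates as being among patients still on treatment, and show n observed / n treated at each visit.
4. State once how the discontinuation-visit mapping (SAP 2.5.4), the inclusion default (SAP 2.1.5) and the on-treatment condition (SAP 2.4.6.1) work together. Apply the rule identically to EOT records that could fall at Week 24 and to the third portion's Week-96 EOT visit.

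The cost is SAP wording and extra tables, with no new data. The added long-term rate will be less favourable than the observed one.

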#### *Non-responder imputation approach:*

In general, number of joints with active arthritis, number of joints with limited range of motion, and at least 3 of the remaining 4 ACR components at baseline and a time point are required to determine responder status.

In this method of missing data handling, the data collected after treatment discontinuation will be set to missing. No imputation of missing post-baseline values will be performed. Responder status will be determined using available data and patients will automatically become non-responders for all time points beyond the time point they discontinued study treatment or for which there is insufficient data.

***LOCF approach:***

In this method of missing data handling (sensitivity analysis), the missing data will be imputed using the last observation carried forward (LOCF) procedure from the point of treatment discontinuation for all 6 ACR components for all visits post that point. Responder status will be determined using the imputed data.

In this approach, patients with insufficient data after imputation (ie, number of joints with active arthritis, number of joints with limited range of motion, and at least 3 of the remaining 4 ACR components) at baseline and a time point will be considered as non-responders at that time point.

***As observed including post discontinuation follow-up:***

All observed data up to week 12, including those collected after treatment discontinuation, will be included in the analysis. No missing data will be imputed.

***Subgroup analyses:***

No additional subgroup summaries are planned for efficacy.

**2.4.6.2 Analyses of other efficacy endpoints**

JIA ACR30 core set variable scores and changes from baseline for each dose regimen cohort and weight group will be summarized by visit using means, standard errors, and corresponding 95% CIs. JIA ACR30 response using ESR instead of hs-CRP will be summarized using the same methods as described in the previous section.

JIA ACR50/70/90/100 responses will be summarized using the same methods as described above for JIA-ACR30.

Overall score and change from baseline in JADAS-27 will be summarized by visit (including number, mean, standard error, SD, median, minimum, and maximum) for each dose regimen cohort and weight group (if possible).

Proportions of patients with the low disease activity ( $JADAS-27 \leq 3.8$ ) and inactive disease activity ( $JADAS-27 \leq 1.0$ ) as defined based on JADAS-27 will be explored and summarized. The Kaplan-Meier plot for time to first onset of achieving low disease activity or achieving inactive disease will also be provided.

For the analyses of continuous endpoints including JIA ACR core set variables and JADAS-27, no data will be imputed and the analyses will be done based on data as observed while the patient remains on treatment.

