1.2.2 Extension phase

In the dose-finding and second portions, only patients achieving at least a JIA ACR30 response at Week 12 will be permitted to continue to participate in the extension phase.

During the extension phase:

- Patients who were enrolled to the selected dose regimen during the core treatment phase (either during the initial dose-finding portion or directly to the selected dose regimen in the second portion) will continue on the selected dose regimen during the extension phase and will be followed-up as noted in [Section 1.2.2.1](#))
- Once the selected dose regimen has been determined, patients who were not assigned to the selected dose regimen will have their dose regimen adjusted to the selected dose regimen during the extension phase. Prior to dose adjustment, these patients will complete the assessments as noted in [Section 1.2.2.1](#). After the dose regimen is determined, the patients will have their dose regimen adjusted to the selected dose regimen at the time of their next regular scheduled visit (according to [Section 1.2.2.1](#)), which will be considered as the first visit (Visit 101 [Week 0]) as shown in the flow chart in [Section 1.2.2.2](#). These patients will then continue with the assessments as noted in [Section 1.2.2.2](#). All patients will remain on treatment until they have received up to a total of 144 weeks of sarilumab exposure calculated from Visit 12. A table to determine when the last on-treatment visit should occur and the weeks between the last on-treatment visit, and the EOT visit based on when the patient was changed to the selected dose regimen is provided in [Table 1](#). After the last on-treatment visit, patients will be scheduled for the EOT visit (Visit 27) and the EOS visit (Visit 28).
- Patients who are enrolled in the third portion with the selected dose regimen will be followed-up as noted in [Section 1.2.2.3](#).

1.2.2.1 Flow chart for patients who remain on the current dose (selected dose regimen) from the dose-finding portion or recruited directly under the selected dose regimen in the second portion

Visit	Extension phase (up to 144 weeks of sarilumab exposure from V12)														Post-treatment follow-up (6 weeks)		
	V13	V14	V15	V16	V17	V18	V19	V20	V21	V22	V23	V24	V25	V26		V27 ^a	V28 ^b

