The 12-week core treatment phase is from Visit 2 (Baseline-Week 0) to the time that Visit 12 investigational medicinal product (IMP) is administered. During the 12-week core treatment phase, for the dose-finding and second portions, patients in the lower weight group (Group B: < 30 kg and ≥ 10 kg) will be randomly assigned to the following sarilumab PK sampling Schedule 1 or 2 ([Section 9.1.1](#)) in order to minimize the amount of blood withdrawn and the number of visits while maintaining the evaluation of the primary endpoint:

- Schedule 1: Baseline, Day 3, Day 8, Week 2, Week 4, Week 8, and Week 12
- Schedule 2: Baseline, Day 5, Day 12, Week 2, Week 4, Week 8, and Week 12.

2. An extension phase:

- A 144-week extension for patients enrolled in the dose-finding and second portions: The IMP at Visit 12 is considered as the first IMP for the extension phase. Only patients who have reached a JIA ACR30 response at Visit 12 (Week 12) will be permitted to continue in the extension phase. Patients will continue on the same dose regimen of sarilumab they were assigned to receive in the 12-week core treatment phase of the study until the selected dose regimen is determined. Once the dose regimen is selected, patients who were not already on this dose regimen will have their dose regimen adjusted to the selected dose regimen and will follow a new visit schedule with more frequent monitoring (for PK, safety, and efficacy) for the first 12 weeks compared to those patients who do not have dose regimen adjusted ([Section 1.2.2.2](#)).
- An 84-week extension for patients enrolled in the third portion. The IMP at Visit 12 is considered as the first IMP for the extension phase.

3. End-of-Treatment (EOT) and End-of-Study (EOS):

- For patients enrolled in the dose-finding and second portions: Patients who discontinue the study treatment prematurely will be assessed using the procedure for the EOT at Visit 27. These patients will be asked to return for the end-of-study (EOS) assessment 6 weeks after the EOT visit (EOT + 6 weeks). For patients who discontinue the study treatment during the 12-week core treatment phase, there will be an additional sarilumab PK assessment 2 weeks after the EOT visit (EOT + 2 weeks) and IL-6 and soluble interleukin-6 receptor (sIL-6R) will be measured at EOT visit. These patients will be asked to perform all the protocol scheduled visits and assessments except sarilumab administration until Visit 12.

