- Collect blood for fasting lipids at Visit 101 (Week 0), Visit 103 (Week 4), and Visit 106 (Week 12)

- Collect blood for hs-CRP from Visit 101 to Visit 106.
- Collect blood for ESR, ANA/anti-dsDNA antibody at Visit 101 (Week 0) and Visit 106 (Week 12)
- Collect blood samples for serum sarilumab (see [Section 9.1](#) and the study flow chart in [Section 1.2.2.2](#)) at Visit 101 (Week 0), Visit 102 (Week 2), Visit 103 (Week 4), Visit 105 (Week 8), and Visit 106 (Week 12)
- Collect blood samples for antibodies to sarilumab (see [Section 9.1](#) and the study flow chart in [Section 1.2.2.2](#)) at Visit 101
- Perform local urine pregnancy test for the female patients who have commenced menstruation prior to exposure to the IMP at each visit (except Visits 102 [Week 2] and 104 [Week 6])
- Dispense the IMP
- Provide home diary for IMP/compliance
- Administer the IMP
 - Patients should be monitored for at least 30 minutes after IMP administration for any signs or symptoms of a hypersensitivity reaction
- Check local tolerability (see [Section 9.3.3](#))
- Schedule the appointment for the next visit

10.1.9.2.2 Visit 107 (Week 16), Visit 108 (Week 20), Visit 109 (Week 24), Visit 110 (Week 32), Visit 111 (Week 40), Visit 112 (Week 48), Visit 113 (Week 60), Visit 114 (Week 72), Visit 115 (Week 84), Visit 116 (Week 96), Visit 117 (Week 108), Visit 118 (Week 120), and Visit 119 (Week 132)

For detailed information on the procedures for patients who change to the selected dose regimen, see the flow chart in [Section 1.2.2.2](#).

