Appendix C Definition of Efficacy and JIA ACR 30/50/70/90/100

In the dose-finding and second portions, patients who do not achieve a JIA ACR30 by the end of the 12-week core treatment phase should be discontinued from the study treatment to receive standard of care as per the Investigator's clinical judgment. Assessment for lack of efficacy may be initiated after the patient has received at least six weeks of study treatments.

The definition for improvement in JIA [ACR Pediatric 30 criteria (Pedi30)] defines $\geq 3/6$ core set variables improved $\geq 30\%$ from baseline with no more than 1/6 worsened by $\geq 30\%$ (3, 22)

The definition for improvement in JIA [ACR Pediatric 50 criteria (Pedi50)] defines $\geq 3/6$ core set variables improved $\geq 50\%$ from baseline with no more than 1/6 worsened by $\geq 30\%$

The definition for improvement in JIA [ACR Pediatric 70 criteria (Pedi70)] defines $\geq 3/6$ core set variables improved $\geq 70\%$ from baseline with no more than 1/6 worsened by $\geq 30\%$

The definition for improvement in JIA [ACR Pediatric 90 criteria (Pedi90)] defines $\geq 3/6$ core set variables improved at least 90% from baseline with no more than 1/6 worsened by $\geq 30\%$

The definition for improvement in JIA [ACR Pediatric 100 criteria (Pedi100)] defines $\geq 3/6$ core set variables improved $\geq 100\%$ from baseline with no more than 1/6 worsened by $\geq 30\%$

ACR JIA Core Set Includes:

- Physician global assessment of disease activity - Visual Analogue Scale (VAS)
- Parent or patient assessment of overall well-being
- Childhood Health Assessment Questionnaire Disability Index (CHAQ-DI)
- Number of joints with active arthritis
- Number of joints with limited range of motion
- Index of inflammation: hs-CRP.

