### Extension part

Following the 12-week core treatment period, for the dose-finding and second portions, patients who have achieved a JIA ACR30 response [REDACTED] will continue in a 144-week extension phase; for the third portion in the pcJIA study, patients will continue in an 84 week extension phase. For patients enrolled prior to the dose selection (ie, dose-finding portion), they will continue on the same dose regimen of sarilumab they were assigned to receive in the 12-week part of the study until the dose regimen is selected. Once the dose regimen is selected, patients who were not already on this dose regimen will have their doses adjusted. The dose (mg) to be administered to a patient will be calculated at baseline and will remain the same throughout the course of the 12-week core part of the study. During the extension phase, however, the patient's weight will be measured at each visit and the dose will be modified (increase only) accordingly. The dose will be capped at 150 mg for dose regimens 1 (q2w) and 3 (qw) and 200 mg (q2w) for dose regimen 2, respectively.

Patients who discontinue the study treatment prematurely will be assessed using the procedure planned for the End of Treatment (EOT) visit. These patients will be asked to return for the End of Study (EOS) assessment 6 weeks after the EOT visit. For EOT during the 12-week core part, there will be an additional PK assessment 2 weeks after the EOT visit for the dose-finding and second portions (not applicable for the third portion in pcJIA study).

The total maximum duration of participation for a patient in these studies will be 166 weeks for patients enrolled in dose-finding and second portions and up to 106 weeks for patients enrolled in the third portion (pcJIA only):

- Up to 4 weeks of screening (maximum 31 days),

- 12 weeks core treatment period,
- Up to 144 weeks extension phase for patients enrolled in dose-finding and second portions and up to 84 weeks extension phase for patients enrolled in the third portion (pcJIA only), and
- 6 weeks post-treatment follow-up.

Beside the ongoing DEC and DMC reviews of PK, PD, safety and efficacy data for futility and dose escalations, two formal interim analyses for the [REDACTED] study and three formal interim analyses for the pcJIA study will be performed. Details are provided in [Section 3](#).

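### The Kaplan-Meier plot of time to low or inactive disease has no rule for patients who stop without the event; its default overstates attainment, because two of three portions remove Week-12 ACR30 non-responders by rule

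*SAP*

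**What the plan says.** **The plot.** SAP 2.4.6.2 explores the proportions of patients at two JADAS-27 thresholds and adds: "The Kaplan-Meier plot for time to first onset of achieving low disease activity or achieving inactive disease will also be provided". It gives no event-time, censoring or competing-event rule. A later sentence, limited to the core set variables and JADAS-27 as continuous endpoints, says "no data will be imputed and the analyses will be done based on data as observed while the patient remains on treatment". The general rule in SAP 2.1.5 uses all efficacy evaluations up to closeout unless otherwise specified.

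**The Week-12 rule.** For the first two portions (dose-finding and second), Protocol 1.2.2 states that "only patients achieving at least a JIA ACR30 response at Week 12 will be permitted to continue to participate in the extension phase". Appendix C adds, for the same portions, that "patients who do not achieve a JIA ACR30 by the end of the 12-week core treatment phase should be discontinued from the study treatment". The third portion has no stated response condition: "for the third portion in the pcJIA study, patients will continue in an 84 week extension phase" (SAP, Extension part).

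**When JADAS-27 is measured.** The protocol flow charts place it at baseline, Week 12, designated extension visits and EOT. The end-of-study visit (Protocol 10.1.11) collects none of its components. SAP 2.5.4 moves a discontinuation visit that falls between two regular visits to the next visit with a planned assessment. For a child stopped just after Week 12, that is Week 24.

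**The concern.** A Kaplan-Meier curve assumes that censored patients would later reach the target at the same rate as those still at risk. Here a response rule decides who leaves at Week 12. ACR30 and JADAS-27 share the physician global, the patient or parent global and an active joint count (71 joints in one, 27 in the other). The children removed are therefore those improving least on the measure being plotted.

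At stake is what the curve means. It may be taken as the cumulative chance that a treated child reaches low or inactive disease. Run by default, it describes a setting in which non-responders stayed on drug and then did as well as the responders.

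The SAP handles discontinuation with care elsewhere. Section 2.4.6.1 sets out non-responder imputation, LOCF and an analysis that includes post-discontinuation data for the ACR responses. Those approaches cover the 12-week core only, while this curve runs across Week 12.

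**Working it through.** The documents state no expected rate, event count or precision for this plot, so there is no planned figure to reproduce.

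**Inputs from the documents.** About 72 patients in the dose-finding and second portions plus 28 in the third make 100, so 72% fall under the rule. At the selected dose, 18 per weight group gives 36 under the rule. Pooled with the 28, that is 36/64 = 56%.

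**Assumptions, not in the documents.** q is the share at target by Week 12 (all of them ACR30 responders). p is the Week-12 ACR30 rate. h is the share of remaining responders who reach the target later. Removed patients never reach it.

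**Formula, cohort fully under the rule:**
- Proportion reaching the target = q + (p − q)h
- One minus Kaplan-Meier = 1 − (1 − q)(1 − h) = q + (1 − q)h
- Excess = (1 − p)h

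Example with q = 0.2, p = 0.8, h = 2/3: one minus Kaplan-Meier is 1 − 0.8 × 1/3 = 73.3%. The proportion is 0.2 + 0.6 × 2/3 = 60.0%. The excess is 13.3 points.

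**Range.** Take h = 0.58 (30% at Week 24, then 40% of the rest: 1 − 0.7 × 0.6) or h = 0.76 (40%, then 60%: 1 − 0.6 × 0.4).

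| Non-responders, 1 − p | Excess, h = 0.58 | Excess, h = 0.76 |
|---|---|---|
| 5% | +2.9 | +3.8 |
| 10% | +5.8 | +7.6 |
| 20% | +11.6 | +15.2 |
| 30% | +17.4 | +22.8 |

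With p = 0.7 and h = 0.8 the excess is 0.3 × 0.8 = +24 points.

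**Pooling with the third portion.** Use 36 patients under the rule, 28 not, and q = 0.2, p = 0.8, h = 2/3. By Week 12, 0.2 × 64 = 12.8 have the event and 0.2 × 36 = 7.2 are removed, leaving 64 − 12.8 − 7.2 = 44 at risk. Later events number 0.6 × 64 × 2/3 = 25.6. One minus Kaplan-Meier is 1 − 0.8 × (1 − 25.6/44) = 66.5%, against (12.8 + 25.6)/64 = 60.0%. The excess is 6.5 points, about half of 13.3. With q = 0.25 and the two h values in the table, this pooling gives +3.1 to +4.0 at 10% non-response and +5.6 to +7.4 at 20%. Pooling the whole study (72% under the rule) gives +4.0 to +5.2 and +7.6 to +9.9.

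**Mapping EOT to Week 24.** In a cohort fully under the rule with q = 0.25, the excess falls to +4.0 to +6.0 at 10% non-response and +8.0 to +12.0 at 20%. It does not vanish.

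**Head-count illustration (assumed counts).** Of 36 patients, 9 reach the target at Week 12, 7 non-responders are removed, 6 reach it at Week 24, 6 at Week 48, and 8 never do. The proportion reaching it is 21/36 = 58.3%.
- Removed patients censored at EOT: 1 − (27/36)(14/20)(8/14) = 70.0%
- EOT mapped to Week 24: 1 − (27/36)(21/27)(8/14) = 66.7%
- Removed patients kept as non-achievers: 1 − (27/36)(21/27)(15/21) = 58.3%

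**The case against.** **The SAP is silent on censoring.** A reader might infer from the on-treatment sentence in SAP 2.4.6.2 that the plan itself censors every stopped patient. The documents do not support that. The sentence is confined to continuous endpoints, and SAP 2.1.5 takes all evaluations up to closeout. This stands: what the text shows is a missing rule. But using every evaluation does not cure the problem, because a removed child has at most an EOT JADAS-27. With nothing added, the method censors that child.

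**The size is assumed and the rule covers only part of the trial.** Both are true. A reader might carry the 13-point example to the whole study, but the third portion is not subject to the rule, and the visit mapping shrinks the excess further. With few non-responders it is about 3 points.

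**Little depends on the plot.** Efficacy is secondary and descriptive, the thresholds are exploratory, and there is no hypothesis testing. The Week-12 JADAS-27 is taken before the rule acts, so Week-12 summaries are unaffected. All of this stands.

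**Treating every discontinuation as a competing event is an estimand choice,** since patients may withdraw for any reason. That is fair, and a reason to write the choice down.

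**Inflammation marker.** A reader might also infer that JADAS-27 mixes markers after a dose switch. Protocol 10.1.9.2 says "Collect blood for ESR, ANA/anti-dsDNA antibody at Visit 101 (Week 0) and Visit 106 (Week 12") but "Collect blood for hs-CRP from Visit 101 to Visit 106", and the SAP allows either marker. That is a separate question. The SAP gives each marker its own formula, no visible text says the marker changes between visits, and the text of SAP 2.4.11 on post-switch data is not visible. It forms no part of this point.

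**Conclusion.** The point holds as a missing rule combined with a named method whose default is biased upward. The bias is zero only if no non-responder is removed or nobody reaches the target after Week 12. If removed patients never reach the target, the excess over the proportion of treated children who do is (1 − p)h in a cohort fully under the rule. That is about +3 to +24 points for 5% to 30% non-response with h between 0.58 and 0.8. It is roughly half that for selected-dose patients pooled with the third portion, and smaller again if the EOT visit is mapped to Week 24. Since p and h are not in the documents, no single figure can be given. The primary PK results and the Week-12 summaries do not change.

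**What to change.** Replace one minus Kaplan-Meier in SAP 2.4.6.2 with a cumulative incidence curve (Aalen-Johansen):
- **Competing event:** permanent treatment discontinuation without the event, including removal under the Week-12 rule. For that rule, keeping removed patients in the risk set as non-achievers to the end of planned follow-up is equivalent.
- **Event:** count an EOT JADAS-27 at target.
- **Censoring:** only at data cut-off, dose switch, or completion of planned treatment (Week 156, or Week 96 in the third portion).
- **Display:** portions 1+2 and portion 3 separately, each with numbers at risk.

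The cost is a few SAP sentences and a standard procedure in the planned software, with no new data. The downside is a less favourable curve.
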